The Pain, and Symptom Care Palliative Care Clinics from which patients will be recruited at U.T. M.D. Anderson Cancer Center, operates out of the Pain and Palliative Care Center. There are 13 examination rooms staffed by 14 physicians and 5 clinical nurses, and 1 advanced practice nurse. Patients will be recruited from the Palliative Care Outpatient Clinic, which serves, on average, 227 patients a month, and the Pain Clinic, which serves about 464 patients a month. Patients will also be recruited from the Thoracic Clinic, which serves about a 1,000 patients a month. Services available through this clinic include thoracic and cardiovascular surgery, thoracic oncology, and radiation oncology. There are a total of 14 examination rooms staffed by 19 physicians and 11 clinical nurses, 7 advanced practice nurses.

Research staff

The research staff in the Department of Palliative Care and Rehabilitation Medicine at UT M.D. Anderson Cancer Center includes a research nurse manager, a biostatistician, two senior research nurses, one research nurse and one clinical data coordinator. Our group has conducted multiple clinical trials related to symptom management, quality of life and communications between patients and physicians.

Eligibility Requirements

Inclusion Criteria. Patients will be eligible to participate in this study if they meet the following criteria:

- Present with 3 or more symptoms during the last 24 hours (pain, fatigue, chronic nausea and anorexia/cachexia, sleep problems, depression or poor appetite) with average intensity of >/= 4 on a 0 to 10 scale, in which 0=no symptom, and 10=worst possible symptom.
- 2. No clinical evidence of cognitive failure as evidenced by MDAS score of 13 or less at baseline.
- 3. Must be 18 years or older.
- 4. No longer a candidate for aggressive anticancer therapy such as receptor blockers (Iressa, etc.). Patients on oral or palliative chemotherapy are eligible for study if approved by primary oncologist prior to inclusion. Patients who are receiving IV chemotherapy are eligible for study if approved by primary oncologist and they have completed 1st cycle of chemotherapy and are deemed stable by primary oncologist. PI will obtain approval from patient's primary oncologist.
- 5. Life expectancy \geq 30 days.
- 6. Must understand and sign written informed consent.

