- 2. The proposed clinical trial will enroll patients. The inclusion criteria include the following: patients present with 3 or more symptoms (pain, fatigue, appetite (anorexia/cachexia), and nausea) during the preceding 24 hours, have an average intensity ≥4 on a 0 to 10 scale, in which 0=no symptom, and 10=the worst possible symptom;; have no clinical evidence of cognitive failure, have normal Memorial Delirium Assessment Scale [MDAS] 13 or > is considered as normal); must be 18 years or older; have life expectancy ≥ 6 weeks; have a negative pregnancy test if women with childbearing potential; must understand and sign written informed consent; have no concurrent steroids or be off steroids for at least 7 days prior to inclusion into study; Exclusion criteria include patients have major contraindication to Dexamethasone, i.e. allergic reaction; are not able to complete the baseline assessment forms and are pregnant or lactating.
- 3. Data collected for the clinical trial will be from patient medical charts, assessment tools and laboratory results. Data will be collected specifically for this research purposes, and existing data from medical charts will be incorporated (i.e., demographic data).
- 4. Patients will be informed that refusing to participate in the study or deciding to terminate their participation will not affect their current treatment plan. The patients will be given a written and verbal description of the study during the informed consent teaching interview. Guidelines regarding Institutional Review Board, Human Rights Protection will be strictly followed.
- 5. Study subjects will sign an IRB-approved written informed consent form after having the study explained to them in person by the physician. Included in this explanation will be a reassurance that lack of participation in the study will not bear a relationship to their care for cancer or its symptoms. Circumstances of obtaining informed consent will be documented in patient medical records. Informed consent will be obtained in the language preference of the potential subject. When necessary, professional translators, and not family members, will obtain written informed consent.

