It is the MDACC policy that all participants in a clinical trial must be registered in PDMS. To register a participant, the PI or research coordinator must enter some demographic data and then answer all the eligibility criteria that are specific for that protocol. The system is programmed with the logic to determine which eligibility criteria are not met based on the Yes/No response of the person registered unless they completely meet all eligibility criteria. This real time, continuous monitoring of participant eligibility increases participant safety by ensuring that only individuals that meet the criteria are enrolled.

PDMS also contains a field that is visible during the participant registration process that indicates the date of the current IRB approved informed consent document. The OPR staff updates this field each time the IRB approves a modification to an informed consent document. The IRB approved informed consent document is stamped dated and signed only when a protocol is activated. No document without the stamp can be used. Stamping, signing and dating the document are the final step in the activation process. Comparing the date on the informed consent document with the date in PDMS enables the registering individual to make sure the correct informed consent document was used.

OPR also uses PDMS as a tool for monitoring participant safety using menus designed for reporting, tracking and reviewing adverse events. All adverse events (AEs) submitted to the IRB are submitted to OPR, which provides the administrative support to the committee. Each AE for a participant treated at MDACC is entered into PDMS in the electronic file for the protocol upon which the participant was enrolled. The AE form and any additional information supplied to OPR are forwarded to an IRB Vice Chair who is responsible for reviewing AEs. In addition to the submitted information, a report is generated from PDMS summarizing all previous AEs submitted for that protocol and supplied to the IRB Vice Chair. This allows the reviewer to see the entire safety history of the protocol and identify trends much sooner than in situations where the safety information is reviewed together only once a year during an IRB review.

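### The MDAS eligibility cut-off runs in opposite directions in the two inclusion lists, so the rules disagree at every score except 13

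*Combined protocol and SAP*

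**What the plan says.** The combined protocol and SAP lists inclusion criteria twice.

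- **Eligibility Requirements, Inclusion Criteria, item 2:** "No clinical evidence of cognitive failure as evidenced by MDAS score of 13 or less at baseline".
- **Protection of Human Subjects, item 2:** the list opens with "The proposed clinical trial will enroll patients. The inclusion criteria include the following". It then asks that patients "have no clinical evidence of cognitive failure" and that their MDAS be normal, adding that "13 or > is considered as normal".

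The evaluation schedule (Table 1) places the MDAS at baseline only. The section on monitoring trial progress and participant safety says that whoever registers a patient must "answer all the eligibility criteria that are specific for that protocol", and that the system blocks a patient who does not meet them all. It does not reproduce the wording loaded for this trial.

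**The concern.** Both lists apply one scale and one threshold to one purpose, keeping out patients with cognitive failure, but the inequality is reversed. A baseline screen read in the wrong direction would admit the patients it is meant to keep out and turn away those it is meant to admit.

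The criterion bears on the quality of the main data. The primary outcome (FACIT-F), pain (BPI) and anorexia (FAACT) are rated by the patient. Nausea is measured with the ESAS, also rated by the patient, although the protocol notes that the instrument allows caregiver completion. The MDAS is the only scored cognitive screen in the schedule and is not repeated, so a baseline misreading would not be picked up by a later MDAS. The conflict also sits in the item that sets out who may give consent.

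**Working it through.** The plan gives no figure to reproduce, and no sample-size or power calculation is involved. The check compares the two rules as sets of scores.

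**Inputs**

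- Rule A (Eligibility Requirements, inclusion 2): admit if MDAS ≤ 13.
- Rule B (Protection of Human Subjects, item 2): normal, so admissible, if MDAS ≥ 13.

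**Comparison**

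| Baseline MDAS | Rule A | Rule B | Same decision? |
|---|---|---|---|
| Below 13 | Admit | Not normal | No |
| Exactly 13 | Admit | Normal | Yes |
| Above 13 | Do not admit | Normal | No |

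The intersection of {MDAS ≤ 13} and {MDAS ≥ 13} is {13}. The decisions are opposite at all other scores.

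**Could it be a text-extraction fault?** Unlikely. The same item shows other inequality signs intact (symptom intensity ≥ 4, life expectancy ≥ 6 weeks), and the MDAS phrase is coherent as it stands. It has an unmatched closing bracket, which suggests loose drafting but does not change the direction.

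**Is one list marked as superseded?** No. The human-subjects item is written as the criteria of this trial and is not part of a change log. The lists do differ elsewhere: life expectancy is at least 30 days under Eligibility Requirements and at least 6 weeks under Protection of Human Subjects, and the qualifying symptom list is shorter in the latter. They appear not to have been kept in step.

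**Can the document itself settle the direction?** No. FACIT-F, ESAS, BPI, FAACT, HADS and PSQI are described; MDAS scoring is not.

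**Is the check of entered patients still useful?** Yes. The Missing Data section reports 43 dropouts out of 115 (43/115 = 37%), so enrolment is well advanced and baseline scores should be on record.

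**The case against.** The strongest reply is that this is a drafting slip in a summary, with little practical consequence. Several parts of it stand.

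- **Operative list.** The numbered criteria under Eligibility Requirements look like the working list. The human-subjects text is a prose summary in a section that seems not to have been updated: under inclusion of women and minorities it says all patients come from the two Houston institutions, while the recruitment and sample-size text adds a hospice. This makes screening under Rule B less likely. It does not remove the conflict, because neither list is marked as governing.
- **Other safeguards.** Both lists require informed consent and exclude patients who cannot complete the baseline forms, and a physician explains the study in person. The human-subjects item also names absence of cognitive failure alongside the MDAS clause. A severely impaired patient would probably be stopped under either list.
- **Registration check.** The system enforces whatever criterion was loaded. That protects the trial only if the loaded direction is the intended one, which the document does not show.

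A reader might go further and infer that the human-subjects version is the wrong one, that cognitively impaired patients were enrolled, and that their FACIT-F data are invalid. The document does not support this. It gives no MDAS scoring from which to tell which version is wrong, and no evidence that anyone was screened under Rule B.

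A reader might also treat the 20 patients planned at Four Seasons Hospice as exposed, since that site has its own IRB approval. The text says only that its IRB reviewed and approved the protocol, which contains both lists. Nothing ties the site's screening to the human-subjects wording.

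**Conclusion.** The contradiction stands and is unresolved: opposite eligibility decisions at every MDAS score except 13. It should be corrected, because it reverses an eligibility threshold in the human-subjects section of an enrolling trial and because the primary and symptom outcomes depend mainly on patients' own ratings.

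Its demonstrated size is limited to the texts. The number of patients affected is unknown and may be zero. Sample size and power do not depend on the criterion, and cytokines and C-reactive protein are laboratory measures, not patient ratings.

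The conclusion assumes that both lists are current, as nothing says otherwise, and that the printed signs are those of the source document. It takes no position on which direction is right.

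**What to change.** 1. State one MDAS rule, with one threshold and one direction, in both Eligibility Requirements (inclusion 2) and Protection of Human Subjects (item 2). The sponsor must choose it. A sentence saying what a high score means would prevent a repeat. Alternatively, replace the human-subjects list with a cross-reference to the numbered criteria, which would also deal with the life-expectancy and symptom-list differences once the sponsor has settled which apply.
2. Confirm that the registration checklist carries that rule, and that all recruiting sites screen against it.
3. List the recorded baseline MDAS scores of all patients already entered and compare them with the rule. Report any that fall on the wrong side as eligibility deviations, and settle how they are handled in the analysis before the treatment code is broken.

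The cost is a one-line amendment and a query on data already collected. No change to the sample size or the analysis methods is needed.
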